4.1 ANALYSIS SETS

4.1.1 Intention-to-treat Set

For each cohort, the intention-to-treat (ITT) set will include all patients enrolled in the study irrespective of whether they have received study medication or not. In practice during the course of this study, no patient has been enrolled and not received treatment. Therefore ITT and Safety sets are the same, and we label this as Safety Set in all outputs.

4.1.2 Safety Set

For each cohort, the Safety Set will include all patients who have received at least one dose of study medication. All tables (demographics, efficacy and safety) will include a summary by the Safety Set.

4.1.3 Analysis sets for efficacy analyses

The Protocol mandates performing the efficacy analysis on “fully evaluable” patients. We clarify below how this will be interpreted in detail, and subsequently refer to this Efficacy Set as “eligible and evaluable”.

4.1.3.1 Eligibility and evaluability

All patients will be considered **eligible** for the cohort identified from the data recorded on the “Cohort Assignment” CRF unless they have a protocol deviation that compromises their efficacy endpoint, as identified in the current version of the Protocol Deviation Plan at the time of the analysis.

A patient will be considered **evaluable** for NPR if they received study drug, have a baseline tumor assessment and at least one tumor assessment post-baseline (per protocol mandated timelines). Specifically, if a single assessment has been performed, this assessment must be performed between days 18 and 66 (inclusive) post Day 1 of study treatment. (This latter restriction does not apply in case there are two or more assessments.)

4.1.3.2 Stage I Efficacy Set

For each cohort, the Stage I Efficacy analysis set is by intention 12 eligible and evaluable patients having reached their Week 18 visit (or to have had their final study data collection before Week 18, e.g. due to death or other reason for study withdrawal). In some cases, due to late reclassification of protocol deviations, there may in practice be a small number fewer or greater than 12 for Stage 1 analysis.

4.1.3.3 Stage II (and Subsequent) Efficacy Set

For each cohort, the Stage II Efficacy analysis set will include all of the eligible and evaluable patients in the corresponding safety population, once all patients in the cohort have reached Week 18 (or terminated the study). Patients will be considered eligible and evaluable for Stage II, independently of eligibility and evaluability assessed at the time of Stage I analysis.

The same analysis set will be used for all subsequent efficacy analyses.

4.2 SUMMARIES OF STUDY CONDUCT

Enrollment, reasons for treatment discontinuation, reasons for study discontinuation and duration of follow up will be summarized for both Safety and Efficacy Sets. For the analysis of “All combined”, a summary of enrollment by protocol-defined cohort will be provided.

Major protocol deviations, as identified in the current version of the Protocol Deviation Plan at the time of the analysis, will be listed (and summarized for “All combined” only).

4.3 SUMMARIES OF TREATMENT GROUP COMPARABILITY

This is a single arm study and, consequently, no formal treatment group comparisons will be conducted. Demographics (age, sex, ethnicity, and race) and disease history will be summarized. Medical history, prior and concomitant therapies data will be summarized for “All combined” only.

4.4 EFFICACY ANALYSIS

The majority of efficacy analyses will be performed on both Efficacy and Safety Sets. Exceptions are: waterfall plots, PFS, DOR and TTP analyses, which are only presented for efficacy analysis sets by convention.

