6. STATISTICAL CONSIDERATIONS AND ANALYSIS PLAN

Statistical analyses will be based on patients with the same individual tumor type and may be based on pre-defined cohorts or on sub-cohorts. Furthermore, if during the conduct of the study, a specific subgroup of patients in a cohort/sub-cohort is identified (e.g. a biomarker positive subgroup) then statistical analysis may be performed based on this subgroup of patients. In general, within section 6, the term cohort is used to refer to a group of patients to be analyzed together (whether this is a cohort, a sub-cohort or a subgroup).

The safety population will be the main population for all analyses (demographics, efficacy and safety) unless otherwise stated. For each cohort, the safety population will include all patients who have received at least one dose of study medication.

For each cohort, the intent-to-treat (ITT) population will include all patients enrolled in the study irrespective of whether they have received study medication or not. The ITT population will be used to summarize disposition data.

The evaluation of each cohort at the end of Stage I and Stage II will be based only on data from fully evaluable patients, defined as patients receiving at least one dose of Atezolizumab and having at least one tumor assessment post-baseline (per protocol mandated timelines).

The per-protocol (PP) population will not be defined due to the small number of patients per cohort, but major protocol deviations will be listed.

The study will be analyzed for the primary efficacy variable at the end of Stage I and Stage II. All cohorts will also be analyzed at Week 24 (6months) and at the end of cohort. In case a cohort is closed before reaching 12 patients (e.g., due to accrual problems), data for that cohort will be listed only or pooled with cohort 10. The end of cohort analysis for each cohort will take place when all patients in that cohort have been followed for survival for a minimum of 24 months after the last patient has been enrolled in the cohort or until all patients have died, withdrawn consent or are lost to follow up, or if the cohort is stopped due to safety or efficacy reasons, or the Sponsor decides to end the cohort, whichever occurs first.

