4.4.1 Primary Efficacy Endpoint

The primary efficacy endpoint for this study is non progression rate (NPR) at 18 weeks.

Week 18 occurs at Study Day 127. Allowing 15 days either side of the exact Week 18 study day, assessments that occur between Study Day 112 and Study Day 142 (inclusive) will be considered as a Week 18 assessment.

Individual patient response at 18 weeks, based on RECIST v1.1, will be categorized as “CR”, “CR (imputed)”, “PR”, “PR (imputed)”, “SD”, “SD (imputed)”, “PD”, “Death in absence of PD”, “Discontinuation in absence of PD” or “Missing” as follows:

1. any patient who recorded PD (as determined by the Investigator) at any post-baseline tumor assessment up to Study Day 142 inclusive, will be classified as “PD”,
2. any remaining patient who died at or prior to Study Day 142 will be classified as “Death in the absence of PD”,
3. any remaining patient will be classified as “CR”, “PR”, or “SD” according to their Investigator-reported tumor assessment data that falls within the window of Study Day 112 – 142 inclusive (taking the worst case if there are two conflicting assessments within the window)
4. for a patient who does not meet any of the above criteria, but who has a nearby later assessment (up to Day 209), the patient will be classified as “CR (imputed)”, “PR (imputed)” or “SD (imputed)” according to the first tumor assessment in the extended window.
5. any remaining patient will be classified as “Discontinuation in absence of PD” if they have an End of Study date prior to Study Day 142 or, otherwise, as “Missing/Out of window”.

Non progression rate (NPR) at 18 weeks is defined as the percentage of patients with “CR”, “CR (imputed)”, “PR”, “PR (imputed)”, “SD” or “SD (imputed)” at 18 weeks. The denominator is all patients in the analysis (thus in this calculation, Death or Discontinuation in the absence of PD, and Missing/Out of window, are, conservatively, effectively treated as PD).

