4. PD, for a patient with an overall tumour response assessment of PD at any visit, and does not meet the criteria for a BOR of CR, PR or SD.
5. Missing, for a patient with an assessment of SD, PR or CR in the first 42 days after start of study treatment and no further tumour assessments thereafter.

Best overall response will summarize the proportion of patients with each best overall response.

Overall response rate (ORR) is defined as the proportion of patients with a BOR of CR or PR.

Clinical benefit rate (CBR) is defined as the proportion of patients with a BOR of CR, PR or SD.

Duration of response (DOR), based on RECIST v1.1, is defined as the time from the first occurrence of a documented objective response (CR or PR) to the time of progression or death from any cause, whichever occurs first. For patients who do not die or experience disease progression before the end of the study or who are lost to follow-up, duration of objective response will be censored at the day of the last tumor

assessment. Note: DOR will not be analysed if there are less than 4 patients available for the analysis.

Progression-free survival (PFS), based on RECIST v1.1, is defined as the time from the first day of study treatment to the first occurrence of disease progression or death from any cause, whichever occurs first. A patient without a PFS event will be censored at the time of the last evaluable tumor assessment or, for patients with no tumor assessment after the baseline visit, at the time of the first day of study treatment plus 1 day.

Time to progression (TTP), based on RECIST v1.1, is defined as time from the first day of study treatment to the first occurrence of progressive disease or death due to disease progression, whichever occurs first. Patients who have not progressed or died due to disease progression at the time of study completion or who are lost to follow-up will be censored at the date of the last evaluable tumor assessment or, for patients with no tumor assessment after the baseline visit, at the time of the first day of study treatment plus 1 day.

Overall survival (OS) is defined as the time from the first day of study treatment to death from any cause. Patients who are still alive at the time of analysis (clinical cut-off) and patients who are lost to follow-up will be censored at the last date they were known to be alive.

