4.4.4.3 Time to event analyses

The time-to-event variables PFS, OS, TTP and DOR will be presented graphically using the Kaplan-Meier (KM) approach. The median survival time and its 95% confidence interval will be presented. Additionally, the estimated survival rate together with its associated 95% confidence interval at 24 weeks, at 6 and 12 months, and at 24 months (for OS only) will be presented.

Duration of response will be evaluated only for patients who achieve CR or PR (and only analysed if there are more than 3 such patients in a cohort).

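### PFS and TTP are presented only on the Efficacy Set, so treated patients who die before a first scan are missing from the only PFS analysis, and SAP 4.4 conflicts with SAP 4.1.2

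*SAP*

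**What the plan says.** SAP 4.4 states that most efficacy analyses are done on both sets and then lists what is not: "Exceptions are: waterfall plots, PFS, DOR and TTP analyses, which are only presented for efficacy analysis sets by convention". Under SAP 4.1.3.1 a patient is evaluable only if they received study drug and "have a baseline tumor assessment and at least one tumor assessment post-baseline (per protocol mandated timelines". A lone post-baseline scan must fall on days 18 to 66, and patients with a deviation that compromises the efficacy endpoint are ineligible. SAP 4.1.3.3 carries the same set into all later efficacy analyses.

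SAP 4.4.3 defines PFS as "time from the first day of study treatment to the first occurrence of disease progression or death from any cause". TTP counts progression or death due to progression. Both endpoints keep a rule that censors patients with no post-baseline assessment one day after first dose. SAP 4.4.4.3 plans Kaplan-Meier curves, medians, and the "estimated survival rate together with its associated 95% confidence interval at 24 weeks, at 6 and 12 months".

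On populations, SAP 4.1.2 says: "All tables (demographics, efficacy and safety) will include a summary by the Safety Set". Protocol section 6 says: "The safety population will be the main population for all analyses (demographics, efficacy and safety) unless otherwise stated". It reserves the narrower set for one purpose: "The evaluation of each cohort at the end of Stage I and Stage II will be based only on data from fully evaluable patients".

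**The concern.** Membership of the Efficacy Set depends on living long enough to be scanned, but the PFS clock starts at first dose. A death before the first scan, due at about week 6 in Protocol Appendix 1, meets the PFS definition, yet the patient is not in the analysis. Leaving such deaths out can only raise the Kaplan-Meier estimate.

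No other planned analysis restores these patients to a PFS curve. SAP 2.2.1 excludes time-to-event analyses from the all-cohorts-combined set, and the only modified RECIST endpoint that the SAP defines is best overall response. SAP 2.3 describes the Month 12 results as input to future trials and early publication. A reader of a cohort's PFS median would not see how many early deaths are absent or what they would change.

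The SAP also disagrees with itself. SAP 4.1.2 covers all tables and names no exception, SAP 4.4 makes several, and the only reason given is convention.

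**Working it through.** **Design figures.** For non-progression rates of 20% and 40%, a type I error of at most 10% and power of at least 80%, a search for Simon's optimal design returns the plan's rule: stop at 2 or fewer of 12, succeed at 8 or more of 25. Exact type I error is 0.0991 and power 0.815. The concern does not dispute this rule. It supplies the 25 evaluable patients and the 40% used below.

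**Who is missing.**

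| Treated patient | Efficacy Set | PFS by definition | TTP by definition |
|---|---|---|---|
| Dies of progression before any scan | out | event | event |
| Dies of another cause before any scan | out | event | censored one day after first dose |
| Alive, never scanned | out | censored one day after first dose | censored one day after first dose |

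Nobody in the Efficacy Set can lack a post-baseline scan, so the one-day censoring rule in SAP 4.4.3 can never apply there. It has a use only if the analysis is run on a wider set.

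**Size.** Inputs: 25 evaluable patients per cohort (SAP 2.2) and *d* treated patients who die before the first scan. The documents do not give *d*, so I assume 0, 1, 3 or 5. I also assume 40% Efficacy Set PFS at week 18, and an exponential curve through that point for the other figures.

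After the first scan:

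- S_safety(t) = S_eff(t) × 25/(25 + d)
- S_eff(24) = 0.40^(24/18) = 0.295
- Safety Set median = 18 × ln(0.5 × (25 + d)/25) / ln(0.40) weeks

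| d | d/(25 + d) | Factor | Week 18 | Week 24 | Median (weeks) |
|---|---|---|---|---|---|
| 0 | 0% | 1.000 | 40.0% | 29.5% | 13.6 |
| 1 | 3.8% | 0.962 | 38.5% | 28.3% | 12.8 |
| 3 | 10.7% | 0.893 | 35.7% | 26.3% | 11.4 |
| 5 | 16.7% | 0.833 | 33.3% | 24.6% | 10.0 |

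With 20% at week 18 instead, the median goes from 7.75 weeks to 7.31 (d = 1) or 5.71 (d = 5).

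**Kaplan-Meier check.** With 25 evaluable patients, d deaths at day 20, and either 0 or 2 living unscanned patients censored at day 2, week-18 PFS is 0.400, 0.385, 0.357 and 0.333 in both cases. Unscanned living patients leave the risk set before any event and do not move the curve. The shift comes from the deaths alone.

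For scale, the exact 95% confidence interval for 10/25 is 21.1% to 61.3%.

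**The case against.** The strongest reply has four parts.

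- **A specific exception overrides a general rule.** SAP 4.4 lists its exceptions, so a programmer knows what to run, and Protocol section 6 lets the plan depart from its default. This is fair as far as it goes. It reduces the conflict with SAP 4.1.2 to a missing cross-reference, but PFS still omits events that its own definition counts.
- **Much of the gap is covered elsewhere.** NPR at weeks 18 and 24 is presented on the Safety Set, and for week 18 the SAP says that "Death or Discontinuation in the absence of PD, and Missing/Out of window, are, conservatively, effectively treated as PD". OS is also on both sets, and all deaths are listed. This stands, and it leaves the curve, the median and the 12-month rate as the part with no counterpart.
- **The size is assumed.** Entry requires ECOG 0 or 1 and life expectancy above 3 months, so *d* may be 0 or 1, and all the shifts are small beside the confidence interval. The smooth medians also depend on the exponential curve. If progression is recorded only at six-weekly scans, S_eff(12) = 0.40^(12/18) = 0.543. That becomes 0.522, 0.503 or 0.485 for d = 1, 2 or 3, so the median stays at the week-18 scan until d = 3 and then drops a full interval. This also stands. The table is an illustration, not a forecast.
- **The two sets differ in more than early deaths.** The Safety Set also brings back patients with endpoint-compromising deviations or a badly timed lone scan. A difference between the two results is therefore not a pure early-death effect. That is correct, and it limits what may be read from the comparison.

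**Conclusion.** The concern holds. PFS on the Efficacy Set alone leaves out deaths that are PFS events by definition, and for TTP it leaves out early deaths due to progression. The early-death component can only bias the estimates upward. The net direction is uncertain because the other exclusions in SAP 4.1.3.1 can act either way.

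Under the stated assumptions, a 40% week-18 rate is overstated by 1.5 to 6.7 percentage points for 1 to 5 unscanned deaths per 25 evaluable patients, and by nothing if there are none. The defect is confined to secondary, descriptive estimates. The Stage I and Stage II rules, OS and NPR do not depend on it. It should be corrected, but it does not threaten the trial's main conclusion.

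**What to change.** Delete PFS and TTP from the exceptions sentence in SAP 4.4, so that both are presented on the Safety Set as well as the Efficacy Set. Add one line saying that the Safety Set result is the one free of the early-death exclusion. DOR and the waterfall plots can stay as they are, because both need post-baseline scans. A short cross-reference in SAP 4.1.2 to those two remaining exceptions would remove what is left of the inconsistency.

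The cost is one SAP sentence, the added line and a re-run of the existing PFS and TTP programs with the Safety Set flag. The endpoint definitions and censoring rules in SAP 4.4.3 already cover unscanned patients, and the Efficacy Set results are kept.

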4.4.1 Primary Efficacy Endpoint

The primary efficacy endpoint for this study is non progression rate (NPR) at 18 weeks.

Week 18 occurs at Study Day 127. Allowing 15 days either side of the exact Week 18 study day, assessments that occur between Study Day 112 and Study Day 142 (inclusive) will be considered as a Week 18 assessment.

Individual patient response at 18 weeks, based on RECIST v1.1, will be categorized as “CR”, “CR (imputed)”, “PR”, “PR (imputed)”, “SD”, “SD (imputed)”, “PD”, “Death in absence of PD”, “Discontinuation in absence of PD” or “Missing” as follows:

1. any patient who recorded PD (as determined by the Investigator) at any post-baseline tumor assessment up to Study Day 142 inclusive, will be classified as “PD”,
2. any remaining patient who died at or prior to Study Day 142 will be classified as “Death in the absence of PD”,
3. any remaining patient will be classified as “CR”, “PR”, or “SD” according to their Investigator-reported tumor assessment data that falls within the window of Study Day 112 – 142 inclusive (taking the worst case if there are two conflicting assessments within the window)
4. for a patient who does not meet any of the above criteria, but who has a nearby later assessment (up to Day 209), the patient will be classified as “CR (imputed)”, “PR (imputed)” or “SD (imputed)” according to the first tumor assessment in the extended window.
5. any remaining patient will be classified as “Discontinuation in absence of PD” if they have an End of Study date prior to Study Day 142 or, otherwise, as “Missing/Out of window”.

Non progression rate (NPR) at 18 weeks is defined as the percentage of patients with “CR”, “CR (imputed)”, “PR”, “PR (imputed)”, “SD” or “SD (imputed)” at 18 weeks. The denominator is all patients in the analysis (thus in this calculation, Death or Discontinuation in the absence of PD, and Missing/Out of window, are, conservatively, effectively treated as PD).

4.4.2 Analysis of the Primary Efficacy Endpoint

The number and percentage of progression-free patients (NPR) at 18 weeks (Stage II) will be presented along with standard 95% (exact binomial, two-sided) confidence intervals for proportions.

4.4.3 Secondary Efficacy Endpoints

Non progression rate (NPR) at 24 weeks is defined as the percentage of patients with “CR”, “CR (imputed)”, “PR”, “PR (imputed)”, “SD” or “SD (imputed)” at 24 weeks.

Week 24 occurs at Study Day 169. Allowing 20 days either side of the exact Week 24 study day, assessments that occur between Study Day 149 and Study Day 189 (inclusive) will be considered as a Week 24 assessment.

Individual patient response at 24 weeks, based on RECIST v1.1, will be categorized as “CR”, “CR (imputed)”, “PR”, “PR (imputed)”, “SD”, “SD (imputed)”, “PD”, “Death in absence of PD”, “Discontinuation in absence of PD” or “Missing” as follows:

1. any patient who recorded PD at any post-baseline tumor assessment up to Study Day 189 inclusive, will be classified as “PD”,
2. any remaining patient who died at or prior to Study Day 189 will be classified as “Death in the absence of PD”,
3. any remaining patient will be classified as “CR”, “PR”, or “SD” according to their Investigator-reported tumor assessment data that falls within the window of Study Day 149 – 189 inclusive (taking the worst case if there are two conflicting assessments within the window),
4. for a patient who does not meet any of the above criteria, but who has a nearby later assessment (up to Day 209), the patient will be classified as “CR (imputed)”, “PR (imputed)” or “SD (imputed)” according to the first tumor assessment in the extended window.

5. any remaining patient will be classified as "Discontinuation in absence of PD" if they have an End of Study date prior to Study Day 189 or, otherwise, as "Missing/Out of window".

Best overall response (BOR), based on RECIST v1.1, for an individual patient, is defined as the best overall response obtained until progressive disease, death or lost to follow up, whichever is the first, as follows:

1. CR for a patient with an overall tumour response assessment of CR at two consecutive visits at least 28 days apart. If applicable, any tumour assessment within the 28 day period must also record CR.
2. PR for a patient with an overall tumour response assessment of PR or CR at two consecutive visits at least 28 days apart without being a CR. If applicable, any tumour assessment within the 28 day period must also record PR or CR.
3. SD, for a patient with an overall tumour response assessment of SD, PR, or CR at one or more visits at least 42 days after start of study treatment, but are not a confirmed CR or PR.
4. PD, for a patient with an overall tumour response assessment of PD at any visit, and does not meet the criteria for a BOR of CR, PR or SD.
5. Missing, for a patient with an assessment of SD, PR or CR in the first 42 days after start of study treatment and no further tumour assessments thereafter.

Best overall response will summarize the proportion of patients with each best overall response.

Overall response rate (ORR) is defined as the proportion of patients with a BOR of CR or PR.

Clinical benefit rate (CBR) is defined as the proportion of patients with a BOR of CR, PR or SD.

Duration of response (DOR), based on RECIST v1.1, is defined as the time from the first occurrence of a documented objective response (CR or PR) to the time of progression or death from any cause, whichever occurs first. For patients who do not die or experience disease progression before the end of the study or who are lost to follow-up, duration of objective response will be censored at the day of the last tumor

assessment. Note: DOR will not be analysed if there are less than 4 patients available for the analysis.

Progression-free survival (PFS), based on RECIST v1.1, is defined as the time from the first day of study treatment to the first occurrence of disease progression or death from any cause, whichever occurs first. A patient without a PFS event will be censored at the time of the last evaluable tumor assessment or, for patients with no tumor assessment after the baseline visit, at the time of the first day of study treatment plus 1 day.

Time to progression (TTP), based on RECIST v1.1, is defined as time from the first day of study treatment to the first occurrence of progressive disease or death due to disease progression, whichever occurs first. Patients who have not progressed or died due to disease progression at the time of study completion or who are lost to follow-up will be censored at the date of the last evaluable tumor assessment or, for patients with no tumor assessment after the baseline visit, at the time of the first day of study treatment plus 1 day.

Overall survival (OS) is defined as the time from the first day of study treatment to death from any cause. Patients who are still alive at the time of analysis (clinical cut-off) and patients who are lost to follow-up will be censored at the last date they were known to be alive.

Modified best overall response (mBOR), based on modified RECIST, for an individual patient, is defined as the best overall response obtained until death or lost to follow up, whichever is the first. The mBOR categories are obtained in the same manner as for the BOR based on RECIST v1.1, as described above.

Modified best overall response will summarize the proportion of patients with each modified best overall response.

